Severity	Variable	Criteria														
Mild -1	PaO ₂ /FiO ₂ Ratio	200 mmHg < PaO ₂ /FIO ₂ ≤ 300 mmHg														
Moderate-2	PaO ₂ /FiO ₂ Ratio	100 mmHg < PaO ₂ /FIO ₂ ≤ 200 mmHg														
Severe-3	PaO ₂ /FiO ₂	Ratio PaO ₂ /FIO ₂ ≤ 100 mmHg														
Death-4	Patient Status	Yes/No														

Clinical Study Code No.: CLI-050000-04	Version No.: 4.0
EUDRACT No.: 2020-002632-75 – IND No: 153286	Date: 02 MAR 2021

	
 - Delta SOFA Score and sub-score components measured on Day 3 and Day 28 or Discharge whichever comes first - Percentage of patients alive and organ failure free (SOFA score=0) at Day 28 or Discharge whichever comes first - Change from baseline in ventilatory parameters [tidal volume (TV), respiratory rate (RR), dynamic compliance (C_{dyn}), static compliance (C_{stat}), positive end-expiratory pressure (PEEP), peak inspiratory pressure (PIP), plateau pressure (P_{plat})] measured at 6-12-24h after each poractant alfa administration up to 72 hours and at similar timepoints in the control group (6, 12, 24, 30, 36, 48, 54, 60 and 72 hours after randomisation) and then every 24 hours until the patient is discharged from the ICU - Change from baseline in blood gas analysis acid-base balance parameters (i.e. pH, pCO₂, pO₂, HCO₃, lactate) measured at 6-12-24h after each poractant alfa administration up to 72 hours and at similar timepoints in the control group (6, 12, 24, 30, 36, 48, 54, 60 and 72 hours after randomisation) and then every 24 hours till the patient is discharged from the ICU. 
Exploratory (to be applied only in patients from UK)
 
The following parameters will be measured at 12, 24, 48, 72 and 96 hrs after start of treatment (first dose in the poractant alfa group and after randomisation in the control group):
 
 - Change from baseline in lowest and dynamic surface tensions (mN/m) from TA samples - Change from baseline in concentrations of surfactant phospholipids (mg/ml) and proteins (ng/ml) from TA samples - Change from baseline in inflammatory indices such as cellular and cytokine (pg/ml) inflammatory markers (e.g. IL-1, IL-6, TNF alpha, IFN gamma and lymphocyte markers) from TA and blood samples
Safety variables	
 - Adverse events (AEs) - Laboratory Parameters (Blood count, bilirubin, creatinine, LDH, D-dimer, CRP (C-Reactive Protein), procalcitonin) - Vital Signs (Blood pressures and pulse rate)

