--	--

Clinical Study Code No.: CLI-050000-04	Version No.: 4.0
EUDRACT No.: 2020-002632-75 – IND No: 153286	Date: 02 MAR 2021

	
 • Change from baseline in PaO₂/FiO₂ at 6 and 12 hours after each treatment and at similar timepoints in the control group will be compared between groups using ANCOVA model including group, age and country as fixed effect and baseline value as covariate. The same analysis will be performed at each additional timepoint. • Percentage of patients alive and with PaO₂/FiO₂ improvement of >20% at 6 and 12 hours following administration of each dose in the treated group and at similar timepoints in the control group will be compared by groups using logistic regression including treatment group, age and country as factors. Difference in the proportions and related 95% confidence interval will be estimated from the model. Patients who die are considered as a failure. The same analysis will be performed at each additional timepoint. • Change from baseline in FiO₂ will be analysed as PaO₂/FiO₂. • Length of ICU stay (days) at Day 28 will be compared between groups will be compared between groups by using the ANOVA model including treatment group, age and country as factors. Patients who die or are mechanically ventilated longer than this period are assigned with 28 days. • Percentage of patients alive and out of ICU at Day 28 using logistic regression including treatment group, age and country as factors. Difference in the proportions and related 95% confidence interval will be estimated from the model. • Delta SOFA Score and sub-score components at Day 3 and Day 28 or Discharge, whichever comes first, will be analysed at each timepoint using ANCOVA model including group, age and country as fixed effect and baseline value as covariate. • Percentage of patients alive and free of organ failure (i.e. SOFA score=zero) at Day 28 or Discharge, whichever comes first will be compared by groups using logistic regression including treatment group, age and country as factors. Difference in the proportions and related 95% confidence interval will be estimated from the model. • Change from baseline in ventilator parameters (TV, RR, Cdyn, Cstat, PEEP, PIP, Pplat) will be summarized by means of descriptive statistics or frequency distribution, as appropriate by group at each timepoint. • Change from baseline in BGA acid-base balance parameters (i.e. pH, pCO₂, pO₂, HCO₃, lactate) will be summarized by means of descriptive statistics by group at each timepoint. 
Exploratory Efficacy Variables (to be applied only in patients from UK)
 
 • Exploratory parameters from TA aspirates and blood samples will be summarized both as absolute values and as change from baseline values by treatment group at each timepoint using descriptive statistics. 
Safety Variables

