4.1.2.2 Others Secondary Efficacy Variables

- Number of days alive and ventilator-free **at Day 28**
- Mortality **at Day 21 and Day 28**
- Number of days alive and free from invasive ventilation **at Day 21 and Day 28**

- Number of days alive and free from non-invasive ventilation (NIV) at **Day 21 and Day 28**
- Percentage of subjects with improvement in severity status defined as a decrease in the severity score at **Day 28 or Discharge**, whichever comes first. Severity score will be defined as Mild, Moderate, Severe or Death based on PaO₂/FiO₂ ratio and subject status at Day 28 and numerically rated from 1-4 respectively:

Severity	Variable	Criteria
Mild -1	PaO ₂ /FiO ₂ Ratio	200 mmHg < PaO ₂ /FIO ₂ ≤ 300 mmHg
Moderate - 2	PaO ₂ /FiO ₂ Ratio	100 mmHg < PaO ₂ /FIO ₂ ≤ 200 mmHg
Severe - 3	PaO ₂ /FiO ₂	Ratio PaO ₂ /FIO ₂ ≤ 100 mmHg
Death - 4	Patient Status	Yes/No

- Change from baseline in PaO₂/FiO₂ ratio at **6 and 12 hours following administration of each dose** in the treated group and at the similar timepoints in the control group (6, 12, 30, 36, 54 and 60 hours after randomisation)
- Change from baseline in PaO₂/FiO₂ ratio at additional timepoints (i.e. every 24 hours after treatment/randomisation until the subject is discharged from the ICU)
- Percentage of subjects alive and with PaO₂/FiO₂ improvement of >20% at **6 and 12 hours following administration of each dose** in the treated group and at similar timepoints in the control group (6, 12, 30, 36, 54 and 60 hours after randomisation)
- Percentage of subjects alive and with PaO₂/FiO₂ improvement of >20% at the additional timepoints (i.e. every 24 hours after treatment/randomisation till the subject is discharged from the ICU)
- Change from baseline in FiO₂ at **6 and 12 hours following administration of each dose** in the treated group and at similar timepoints in the control group (6, 12, 30, 36, 54 and 60 hours after randomisation)
- Change from baseline in FiO₂ at additional timepoints (i.e. every 24 hours after treatment/randomisation until the subject is discharged from the ICU)
- Length of ICU stay (days) **at Day 28**. Subjects who die or are mechanically ventilated longer than this period are assigned with 28 days
- Percentage of subjects alive and out of ICU **at Day 28**
- Delta SOFA Score and sub-score component measured on **Day 3 and Day 28 or Discharge** whichever comes first

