9.3.10 Change from Baseline in SOFA Score

SOFA sub-score and total score actual values and change from baseline will be presented using descriptive statistics at Day 3, ICU discharge or Day 28 (whichever comes first).by treatment group. The change from baseline to Day 3 and to ICU Discharge or Day 28 difference between the two groups for each sub-score and for total score will be described.

A graph displaying the means and SD for each timepoint (until the subject is discharged from ICU) will be also provided for each treatment group.

9.3.11 Percentage of Subjects Alive and Organ Failure Free (SOFA score=0) at Day 28 or Discharge

The subject will be defined alive and organ failure free at Day 28 or Discharge if:

- Date of Death is missing or > MIN (Date of Day 28 or Date of Discharge)

AND

- Total SOFA Score = 0 at Day 28 or at Discharge

The percentage will be summarized.

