Table 14.2.10	Summary of Actual Values and Change from Baseline in FiO2 at Each Timepoint (Intention-To-Treat Set)	TPT001	
 - Overall column should not be displayed. - Remove '95% CI for Mean', 'n geometric', 'Geometric mean' categories. 	Add the footnote: [1] Duplicated data reported twice at 2 different timepoints are reported at the first occurrence for post dose/post randomisation and at the last occurrence for pre dose/pre randomisation. Source: Listing 16.2.6.2-a
Table 14.2.11	Summary of Length of ICU Stay (Days) at Day 28 (Intention-To-Treat Set)	TPT001	
 - Overall column should not be displayed. - ICU stays (days) have to be display by stay and in total (see SAP section 9.3.8) - one row by stay and total for each considered subject. For example : First Stay: Duration (Days), Second Stay: Duration (Days), Total: Duration (Days) - Remove '95% CI for Mean', 'n geometric', 'Geometric mean' categories. 	Add the footnotes: [1] The length of ICU stay (days) is calculated as MIN (date of ICU discharge, date of Day 28) – date of ICU entrance + 1. [2] Subjects who die or are mechanically ventilated longer than this period are assigned with 28 days. Source: Listing 16.2.6.2-b

Table Number	Table Title	Template Code	Notes	Footnotes/Source Listing Number
Table 14.2.12	Summary of Proportion of Subjects Alive and Out of ICU at Day 28 (Intention-To-Treat Set)	TPT006	
 - There is only one timepoint to display: Day28. - Do not present 'At Any timepoint' line. - Do not display 'Visit' on the title line. 	Source: Listing 16.2.6.2-b
Table 14.2.13	Summary of Actual Values and Delta SOFA Score and Sub-Score from Baseline (Intention-To-Treat Set)	TPT001	
 - Replace 'Visit' by 'Timepoint' with categories: Day 3, ICU Discharge, Day 28. - Remove '95% CI for Mean', 'n geometric', 'Geometric mean' categories. - Overall column should not be displayed. 	Source: Listing 16.2.6.3
Table 14.2.14	Summary of Proportion of Subjects Alive and Organ Failure Free at Day 28/Discharge (Intention-To-Treat Set)	TPT006	
 - There is only one timepoint to be display: Day28/Discharge. - Do not present 'At Any timepoint' line. - Do not display 'Visit' on the title line. 	Add the footnote: [1] Organ Failure Free is defined as a SOFA score =0 Source: Listing 16.2.6.3

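### The Table 14.2.13 shell splits the single late SOFA timepoint into ICU Discharge and Day 28 rows, so no planned table or figure shows delta SOFA at the timepoint the endpoint defines

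*SAP*

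**What the plan says.** The endpoint has two timepoints: Day 3 and one late value. SAP 4.1.2.2 words it as "Delta SOFA Score and sub-score component measured on Day 3 and Day 28 or Discharge whichever comes first". The Protocol Outline and Protocol section 8 list it the same way, and the analysis text in the Outline and Protocol 12.3.5 reads "Delta SOFA Score and sub-score components at Day 3 and Day 28 or Discharge, whichever comes first, will be analysed at each timepoint". SAP 9.3.10 keeps the earlier-of-the-two rule and adds that the change "to ICU Discharge or Day 28 difference between the two groups for each sub-score and for total score will be described".

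The shell for Table 14.2.13 in SAP 16.1 lists three categories: "Replace 'Visit' by 'Timepoint' with categories: Day 3, ICU Discharge, Day 28". The next SOFA shell, Table 14.2.14, has the same late timing and says "There is only one timepoint to be display: Day28/Discharge". Tables 14.2.7.1 and 14.2.7.2 (severity status) also use one combined Day 28/Discharge category. Figure 14.2.3 takes Table 14.2.13 as its source.

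The schedules (Protocol 7.1; SAP Table 1) take SOFA at screening, at about 72 hours, at ICU discharge, and at Day 28 only if the patient has not left ICU. SAP 7.4 does not impute missing values and summarises only those observed.

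**The concern.** On the schedules, the ICU Discharge row holds patients who left ICU and the Day 28 row holds those still there. Leaving ICU is an outcome of this trial: length of ICU stay and being alive and out of ICU at Day 28 are both secondary endpoints. A treatment that gets more patients out of ICU changes who is in each row, so the arms are no longer comparable within a row. Part of the benefit lies in the move from one row to the other, and neither row mean counts that move.

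SAP section 12 drops the formal SOFA analysis but still names its timing as Day 3 and Day 28/Discharge. It does not declare a split. Since the efficacy output is now descriptive only, the shell largely decides what a reader of the report sees for this endpoint.

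**Working it through.** The documents give no SOFA means, SDs or discharge rates, so there is no stated SOFA figure to reproduce. The mismatch itself rests on the text. The calculations below only show what it can do.

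**Inputs from the documents:** planned size 42 and 28 (SAP 5); expected ICU mortality 30–70% (Protocol 1.1). **Assumed:** everything else.

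**1. Row sizes.** With mortality m and a share d of survivors discharged by Day 28 (assumed 40–80%), the ICU Discharge row has n(1−m)d patients and the Day 28 row n(1−m)(1−d).

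| Row | Poractant alfa | Control |
|---|---|---|
| ICU Discharge, largest (m 0.3, d 0.8) | 42×0.7×0.8 = 23.5 | 28×0.7×0.8 = 15.7 |
| ICU Discharge, smallest (m 0.7, d 0.4) | 42×0.3×0.4 = 5.0 | 28×0.3×0.4 = 3.4 |
| Day 28, largest (m 0.3, d 0.4) | 42×0.7×0.6 = 17.6 | 28×0.7×0.6 = 11.8 |
| Day 28, smallest (m 0.7, d 0.8) | 42×0.3×0.2 = 2.5 | 28×0.3×0.2 = 1.7 |

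The real rows will be smaller in total, because recruitment stopped before 70 (SAP 12).

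**2. Simple mixture.** Let mean delta SOFA be -6 in discharged patients and -1 in those still in ICU, the same in both arms. Both split rows then show a difference of 0. With a share p discharged, the combined mean is -6p - 1(1-p) = -1 - 5p, so the combined difference is -5 × (p treated - p control):

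- 50% control, 60% treated: -0.5
- 50% control, 70% treated: -1.0
- 40% control, 70% treated: -1.5

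**3. Graded severity.** Let a latent recovery score L be normal with SD 1, mean 0 in control and s in treated, with delta SOFA = -3 - 3L. Patients below a lower cut die and those above an upper cut are discharged. The cuts give control mortality of 30, 50 or 70% and 40, 60 or 80% of control survivors discharged. Taking s = 0.25 or 0.5 makes the true shift -0.75 or -1.5. The mean of L between cuts a and b is μ + [φ(a−μ) − φ(b−μ)] / [Φ(b−μ) − Φ(a−μ)], where μ is the arm mean. Across the 18 scenarios the treated-minus-control differences are:

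- ICU Discharge row: -0.15 to -0.69
- Day 28 row: 0.00 to -0.15
- Combined row of survivors: -0.21 to -0.85

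In every scenario each split row is nearer zero than the combined row.

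**4. Reversal is possible.** Take 20 survivors per arm. Control: 11 discharged at -6; 4 in ICU at -2 and 5 at 0. Treated: the same, except that the 4 borderline patients are discharged at -4.

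- ICU Discharge row: control -66/11 = -6.0; treated (-66 - 16)/15 = -82/15 = -5.47
- Day 28 row: control -8/9 = -0.89; treated 0/5 = 0
- Combined: control (-66 - 8)/20 = -3.7; treated -82/20 = -4.1

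Both rows favour control and the defined value favours poractant alfa. The example was built to do this.

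**The case against.** The best defence is that only a shell note is out of line. SAP 9.3.10 is the governing analysis text and keeps the combined rule, and Listing 16.2.6.3 holds every patient's SOFA values. If the rows do not overlap, their n and mean give back the combined mean: in step 4, (15×(-5.47) + 5×0)/20 = -4.1. Table 14.2.12 also reports the proportion alive and out of ICU. All of this stands, so it would be wrong to infer that the defined value is lost or absent from every output. It is absent from the table and figure shells. A reader should not have to rebuild it, and the median cannot be rebuilt from the two rows.

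Non-overlap is not certain either. Protocol 7.1.5 lists SOFA at Day 28 for patients who remain in hospital, which is wider than the schedules. A ward patient could then have a value in both rows.

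Other stronger readings also fail:

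- **The table will reverse the treatment effect.** Nothing in the documents supports this. Reversal appeared only in a constructed example, and the other scenarios gave attenuation.
- **The split causes deaths to drop out.** Patients who die in ICU before Day 28 have no late SOFA value in a combined row either. The composite strategy in SAP 7.2 covers binary endpoints only.
- **The shell for Figure 14.2.3 names the split categories.** It does not. It could only take them from its source table.

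**Conclusion.** The point holds as an inconsistency between the endpoint definition and a table shell. The planned table does not report delta SOFA at its defined late timepoint, and its two late rows compare the arms within outcome-selected subsets. The likely effect is a contrast nearer zero than the defined one. In the illustrations the gap is up to 1.5 SOFA points under the simple mixture and smaller under graded severity. These sizes rest on assumed SOFA changes and discharge rates and show what can happen, not what will.

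The reach is limited to one descriptive secondary endpoint in a trial that closed early. The Day 3 row, the primary and key secondary endpoints, and all tests and p-values are untouched. A combined row restores the defined endpoint but does not make the comparison free of selection, since it still covers only patients alive at the late timepoint.

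**What to change.** - In Table 14.2.13 add a derived row for ICU discharge or Day 28, whichever is earlier, matching the single category in Table 14.2.14. Show by arm the number contributing and the number with no value because of death. Label the row as covering patients alive at that timepoint.
- Use Day 3 and this derived timepoint in Figure 14.2.3, and replace the figure's note, which refers to itself, with explicit categories.
- Keep the separate ICU Discharge and Day 28 rows if wanted, marked as supplementary.
- Reconcile Protocol 7.1.5 with the schedules in Protocol 7.1 and SAP Table 1 on who has a SOFA at Day 28. The earlier-of-the-two rule then gives one late value per patient.

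The cost is shell wording and one derived timepoint. No new data are needed and no planned summary is lost.

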16.2 Listings

Listings will include data at observed Timepoints only, without imputation for missing data.

Listing Number	Listing Title	Template Code	Notes	Footnotes
Listing 16.1.7	Randomisation Schedule (Enrolled Set)	DSL001		
Listing 16.2.1.1	Subjects Disposition (Enrolled Set)	DSL004	
- 'Period of last intake of study treatment' and 'Last treatment received' columns not to be displayed.- Date of first and last doses are fulfilled only for poractant alfa group.	
Add the following footnotes:
 
[1] [Day 1] is the study Day at Date of Study Discontinuation calculated with reference to the Informed Consent Date
 
[2] [Day 2] is the study Day at Date of Study Discontinuation calculated with reference to the First Dose
 
[3] [Day 3] is the study Day at Date of Study Discontinuation calculated with reference to the Last Dose Date

Listing Number	Listing Title	Template Code	Notes	Footnotes
Listing 16.2.1.2	Study Visits (Intention-To-Treat Set)	SVL001	
 - Remove the word 'Retest' in header. 	Ass the footnote: [1] [Study Day] is the study Day at Visit calculated with reference to the randomization Date
Listing 16.2.2.1	Violation of Eligibility Criteria (Enrolled Set)	DVL001	
 - Only deviations from DV in relation to inclusion/exclusion criteria. - Change 'Visit' to 'Timepoint'. - Remove 'Reference analysis set' column. 	
Listing 16.2.2.2	Protocol Deviation (Enrolled Set)	DVL002	
 - Include all deviations from DV. - Remove 'Randomised sequence', 'Period', and 'Reference analysis set' columns. 	
Listing 16.2.3.1	Analysis Sets Disposition (Enrolled Set)	DSL006	
 - Remove 'Period' and 'Randomised sequence' - Include Safety Set and ITT Set 	
Listing 16.2.3.2	Exclusion from Safety and Intention-To-Treat Sets (Enrolled set)	DSL007	
 - Remove 'Period' and 'Randomised sequence' - Include reason for exclusion from safety set and form ITT sets 	
Listing 16.2.4.1	Demographic Characteristics (Intention-To-Treat Set)	DML001	
 - Remove 'Ethnicity' column. 	
Listing 16.2.4.2	SARS-COV-19 ARDS History (Intention-To-Treat Set)	SCL001	The following columns will be presented: 
 - Subject ID - Treatment Group - Date of Positive SARS-COV-19 rt-PCR - ICU Admission Date - Intubation Date/Time - Medication Category 	

Listing Number	Listing Title	Template Code	Notes	Footnotes
Listing 16.2.4.3	Other Baseline and Disease Characteristics (Intention-To-Treat Set)	DML001	The following columns will be presented: - Subject ID - Treatment Group - SBP (mmHg) - DBP (mmHg) - Pulse Rate (bpm) - PaO ₂ /FiO ₂ ratio (mmHg) - FiO ₂ (%) - SOFA Score	
Listing 16.2.4.4	Medical and Surgical History (Intention-To-Treat Set)	MHL001		Add the footnote: [1] System Organ Class and Preferred Term are coded using MedDRA Version 23.0.
Listing 16.2.4.5	Concomitant Diseases (Intention-To-Treat Set)	MHL002		Same as Listing 16.2.4.4
Listing 16.2.4.6	Procedures (Intention-To-Treat Set)	PRL001	- Remove 'Analysis Period' in the header - [CAT]: Prior, Maintained, And Concomitant. - Drop the last column 'Indication'	Add the footnote: [1] System Organ Class and Preferred Term are coded using MedDRA Version 23.0.
Listing 16.2.4.7	Medications (Intention-To-Treat Set)	CML001	- Remove 'Analysis Period' In the header - [CAT]: Prior, Maintained And Concomitant.	Add the footnote: [1] ATCs and Preferred Name are coded using WHO-DD March 2020. [2] [Day] is the study Day at Start Date calculated with reference to the First Dose Date

Listing Number	Listing Title	Template Code	Notes	Footnotes
Listing 16.2.4.8	Thoracic CT or Chest X-Ray (Intention-To-Treat Set)	PEL001	
 - Remove Analysis Period column - Display 'Assessment date/Time [Study Day]' instead of 'Assessment date/time [study day / study day in period]' - Display 'Procedure' instead of Body System' 	
Listing 16.2.5	Study Drug Administration (Intention-To-Treat Set)		
The following columns will be presented:
 
 - Subject ID - Randomized Treatment - Actual Treatment - Kit Number - Timepoint - Date/Time of Administration [Day] - Planned Vol. to be Admin. (ml) - Planned Vol. to be Admin. after Dilution (ml) - Actual Diluted Vol. Admin. (ml) - Administration Interrupted 
Only poractant alfa group should have data listed.
	
Listing 16.2.6.1	Ventilatory Support (Intention-To-Treat Set)		
The following columns will be presented:
 
 - Subject ID - Randomized Treatment - Actual Treatment - Ventilator Type - Start Date/Time [Day] - Stop Date/Time [Day] or Ongoing - Duration of Ventilatory Support (Days) – displayed by Type of Support (Invasive or Not Invasive) - Overall Duration of Ventilator Support 	Add the footnotes: [1]: Duration of ventilatory support have been calculated as the difference between end date and start date +1. [2]: Overall duration of ventilatory support has been calculated as the difference between the maximum end date (between invasive and non-invasive ventilation) and start date +1.

Listing Number	Listing Title	Template Code	Notes	Footnotes
Listing 16.2.6.2-a	Ventilatory Parameters by Timepoint (Intention-To-Treat Set)	VSL002	
 - Remove 'Analysis Period' - Display 'Assessment date/Time [Study Day]' instead of 'Assessment date/time [study day / study day in period]' - Do not display [H] flag in Change from baseline column - Skip the last column (Change from pre-dose) - In Test <Unit> column, display: 
 - FiO2 (%) - Mean Arterial Pressure (mmHg) - Dynamic Compliance (ml/cmH₂O) - Static Compliance (ml/cmH₂O) - PaO₂/FiO₂ Ratio - Tidal Volume (ml/kg BW) - Respiratory Rate (/min) - Peak Inspiratory Pressure - PIP (cmH₂O) - Plateau Pressure (cmH₂O) - Positive End-Expiratory Pressure - PEEP (cmH₂O) - Blood Flows (L/min) - Sweep Gas Flows (L/min) - Add a last column displaying PaO₂/FiO₂ Ratio Improvement (<20%, >=20% or death) 	Add the footnotes: [1]: Baseline=Y flags baseline value [2]: Use=Y: included in the analysis [3] Duplicated data reported twice at 2 different timepoints are reported at the first occurrence for post dose/post randomisation and at the last occurrence for pre dose/pre randomisation.

Listing Number	Listing Title	Template Code	Notes	Footnotes
Listing 16.2.6.2-b	Ventilatory Derived Parameters by Timepoint (Intention-To-Treat Set)	-	
 - Display: - Subject ID - Randomized Treatment - Actual Treatment - Parameter <Unit> 
 - Number of Days Free From Invasive Ventilation - Number of Days Free From Non-invasive Ventilation - Mortality - Number of Days Alive and Ventilator-free - Alive and Free of Respiratory Failure - Alive and Out of ICU - Length of Primary ICU Stay (Days) - Length of Secondary ICU Stay (Days) - Length of Total ICU Stay (Days) - Alive and Organ Failure Free - Severity PaO₂/FiO₂ ratio - Improvement in Severity PaO₂/FiO₂ ratio - Values (display one column for Baseline, one for D21 and one for D28 results) 
Add the following Flags as relevant at D21 and/or D28 results:
 
 - Min 12H Ventil. Free - Min 12H Inv. Ventil. Free - Min 12H NInv. Ventil. Free 	Add the footnotes: 
 [1] * Flag subject with minimum 12H of ventilation free [2] ^ Flag subject with min 12H of NIV free [3]# Flag subject with minimum 12H of IV free

Listing Number	Listing Title	Template Code	Notes	Footnotes
Listing 16.2.6.3	SOFA Score (Intention-To-Treat Set)	VSL002	
 - Remove 'Analysis Period' - Display 'Assessment date [Study Day]' instead of 'Assessment date/time [study day / study day in period]' - Do not display [H] flag in Change from baseline column - Skip the last column (Change from pre-dose) - Do not display the unit in column 'Test' (no unit for SOFA score) - In Test column, display: 
 - Respiratory system Score - Nervous system Score - Cardiovascular system Score - Liver Score - Coagulation Score - Kidney Score - SOFA Score (derived) 	Add the footnotes: [1]: Baseline: Y flags baseline value [2]: Use=Y: included in the analysis
Listing 16.2.6.4	Blood Gas Analysis (Intention-To-Treat Set)	VSL002	
 - Remove 'Analysis Period' - Display 'Assessment date/Time [Study Day]' instead of 'Assessment date/time [study day / study day in period]' - Do not display [H] flag in Change from baseline column - Skip the last column (Change from pre-dose) - In Test <Unit> column, display: 
 - pH - pCO2 (mmHg) - paO2 (mmHg) - HCO3 (mmol/L) - Lactate (mmol/L) 	Add the footnotes: [1]: Baseline: Y flags baseline value [2]: Use=Y: included in the analysis [3] Duplicated data reported twice at 2 different timepoints are reported at the first occurrence for post dose/post randomisation and at the last occurrence for pre dose/pre randomisation.

Listing Number	Listing Title	Template Code	Notes	Footnotes
Listing 16.2.6.5	Hospitalization (Intention-To-Treat Set)		Variables to be listed: - Subject ID - Randomized Treatment - Hospitalization Type - Admission Date/Time [Day] - Discharge Date/Time [Day] - Hospital Stay (days) - Hospital Transfer (Date [Day]/Destination)	Add the footnote: [1] Hospital Stay has been calculated as the difference between discharge date and admission date +1.
Listing 16.2.6.6	Tracheal Aspirate and Blood Samples (Intention-To-Treat Set)	LBL001	- Remove 'Analysis Period' - Display 'Assessment date/Time [Study Day]' instead of 'Assessment date/time [study day / study day in period]' - Do not display CSA [4] column - Add a column with LBSPEC 'Sample from' with Tracheal Aspirate and blood as value - In Test <Unit> column, display: Surfactant Function measuring surface tension (mN/m) from TA samples. - Mass spec lipid analysis (%) from TA samples. - Protein D Enzyme Linked Immunosorbent Assay (ng/mL) from TA samples. - Surfactant Protein D Enzyme Linked Immunosorbent Assay (ng/mL) from Blood samples. - Cytospin from TA samples There is no normal range for TA aspirates samples, Normal range and ABN column will remain empty.	Add the footnotes: [1] Baseline=Y flags baseline value [2] USE=Y: included in the analysis [3] H = Abnormally High Value / L = Abnormally Low Value, compared to the Normal Range. [4] No Normal range for tracheal aspirate samples [5] ND: Not Done, BLOQ: Below the lower limit of quantitation

Listing Number	Listing Title	Template Code	Notes	Footnotes
Listing 16.2.7.1	Pre-treatment Adverse Events (Intention-To-Treat Set)	AEL001	
 - Remove 'Ethnicity', 'Pattern'. - Replace 'Concomitant Therapy' 'Concomitant Procedure' by 'Concomitant Therapy / Concomitant Procedure' - Concatenate AEACN with AEACNOTH (Action taken : <specify>) 	Add the footnotes: [1] CA = Is a congenital anomaly or birth defect; DI = Results in persistent or significant disability or incapacity; DTH = Results in death; HSP = Requires hospitalization or prolongation of existing hospitalization; LTH = Is life-threatening; SIG = Is a medically significant adverse event. [2] System Organ Class and Preferred Term are coded using MedDRA Version 23.0.
Listing 16.2.7.2	Treatment Emergent Adverse Events (Intention-To-Treat Set)	AEL002	
 - Remove 'Ethnicity', 'Period/Actual Treatment', 'Starting dose/dose at onset/weight' and 'Pattern'. - Replace 'Concomitant Therapy' 'Concomitant Procedure' by 'Concomitant Therapy / Concomitant Procedure' - Concatenate AEACN with AEACNOTH (Action taken : <specify>) 	Same as Listing 16.2.7.1
Listing 16.2.7.3	Serious Treatment Emergent Adverse Events (Intention-To-Treat Set)	AEL002	Same as Listing 16.2.7.2	Same as Listing 16.2.7.1
Listing 16.2.7.4	Non-Serious Treatment Emergent Adverse Events (Intention-To-Treat Set)	AEL002	Same as Listing 16.2.7.2	Same as Listing 16.2.7.1

Listing Number	Listing Title	Template Code	Notes	Footnotes
Listing 16.2.7.5	Treatment Emergent Adverse Drug Reactions (Intention-To-Treat Set)	AEL002	Same as Listing 16.2.7.2	Same as Listing 16.2.7.1
Listing 16.2.7.6	Serious Treatment Emergent Adverse Drug Reactions (Intention-To-Treat Set)	AEL002	Same as Listing 16.2.7.2	Same as Listing 16.2.7.1
Listing 16.2.7.7	Severe Treatment Emergent Adverse Events (Intention-To-Treat Set)	AEL002	Same as Listing 16.2.7.2	Same as Listing 16.2.7.1
Listing 16.2.7.8	Treatment Emergent Adverse Events Leading to Study Drug Discontinuation (Intention-To-Treat Set)	AEL002	Same as Listing 16.2.7.2	Same as Listing 16.2.7.1
Listing 16.2.7.9	Treatment Emergent Adverse Events Leading to Death (Intention-To-Treat Set)	AEL002	Same as Listing 16.2.7.2	Same as Listing 16.2.7.1
Listing 16.2.8.1	Vital Signs (Intention-To-Treat Set)	VSL001	
 - Remove 'Analysis Period' column. - Remove 'Study day in Period'. - Change 'Analysis Timepoint' to 'Timepoint'. - Change 'Body Weight (kg)' to 'Pulse Rate' and put as last column. - Do not display 'CHG [3]' (Change from pre-dose) 	Add the footnotes: [1] Use=Included in the Analysis; B: Flags Baseline value [2] CFB is Change from Baseline [3] Duplicated data reported twice at 2 different timepoints are reported at the first occurrence for post dose/post randomisation and at the last occurrence for pre dose/pre randomisation.

Listing Number	Listing Title	Template Code	Notes	Footnotes
Listing 16.2.8.2	Laboratory Results: Haematology (Intention-To-Treat Set)	LBL001	
 - Remove 'Analysis Period' column. - Remove 'Study day in Period'. - Change 'Analysis Timepoint' to 'Timepoint'. - Remove 'Fasted' column - Remove 'CSA' column. 
In case of original unit missing, do not display the value.
	Add the footnote: [1] Value with original unit missing are not displayed.
Listing 16.2.8.3	Laboratory Results: Chemistry (Intention-To-Treat Set)	LBL001	Same as Listing 16.2.8.1	Add the footnote: [1] Value with original unit missing are not displayed.
Listing 16.2.8.4	Physical Examination (Intention-To-Treat Set)	PEL001	
 - Remove 'Analysis Period' column. - Remove 'Study day in Period'. 	
Listing 16.2.9	Comments (Intention-To-Treat Set)	COL001	Variables to be listed: 
 - Subject ID - Randomized Treatment - Assessment - Comment 	

